**Background (Include relevant experience, gaps in current knowledge, preliminary data, etc.):**

S pneumoniae is the leading bacterial cause of pneumonia and invasive pneumococcal disease and is a significant cause of morbidity and mortality in the United States with \$16.2 billion dollars spent in healthcare-related costs in 2013¹. The CDC currently recommends the polysaccharide PPSV23 vaccination (Pneumovax®) in all adults over the age of 65 as well as in individuals with chronic lung disease.

Pneumococcal conjugate vaccine PCV13 (Prevnar ®), initially developed for use in children, is currently recommended for immunocompromised adults and individuals with cerebrospinal fluid leaks and cochlear implants. There is some debate as to whether PPSV23 leads to a decrease in prevalence of disease caused by *S. pneumoniae*, indeed, a 2009 meta-analysis funded by the WHO found that the evidence supporting its use was poor.² In 2014, vaccination guidelines changed to support the use of PCV13 in patients over the age of 65 after it was found to be efficacious in preventing community acquired pneumonia and invasive pneumococcal disease in the elderly population.³ The PCV13 vaccine contains polysaccharide antigens conjugated with a protein carrier whereas the PPSV23 contains polysaccharide antigens alone. It is proposed that the conjugate vaccine induces immunity via a T-cell dependent process. Given that patients with asthma are disproportionately affected by pneumococcal disease, it is imperative that the vaccination strategy for pneumonia be as immunogenic and efficacious at eliciting a robust immune response as possible.

To address this, we propose to compare the response to PPSV23 with a novel schedule of PCV13 followed by PPSV23 given eight weeks later in adult patients with asthma. We will assess the immune system at 8 weeks and 16 weeks post vaccination. Given that the PCV13 vaccine elicits immunity via a T-cell dependent mechanism, we hypothesize that giving PCV13 in conjunction with PPSV23 will lead to an enhanced immune response in asthmatic patients.

References

1. American Lung Association. Trends in Pneumonia and Influenza Morbidity and Mortality. November 2015.

Study Design and Methods**Methods: Describe, in detail, the research activities that will be conducted under this protocol:**

Subjects: 50 adult patients diagnosed with asthma will be recruited from patients seen in the Division of Allergic Diseases and from Primary Care; volunteers will also be solicited with flyers and electronic announcements. The patients recruited will be between 19 and 64 years of age. Exclusion criteria include

research exemption requested, history of PCV-13 vaccination, age \leq 19 or \geq 64, history of cochlear implant, CSF leak, CHF, DM, CKD, HIV, CVID as well as patients who have received the PPSV23 vaccine in the last 5 years. Women who are pregnant will also be excluded from the study. They will be contacted at the end of their visit to discuss enrollment in the study by the research coordinator.

Protocol: The patients will then be randomized into either Group A (standard of care) or Group B (experimental group). At the week 0 time point, the patients will receive either PPSV23 vaccine (Group A) or PCV13 (Group B) and undergo a blood draw of 5mL for assessment of pre-vaccination serotype titers. Group A will undergo a 5mL draw for assessment of titers at week 8, 16, and 24 following vaccination. Group B will undergo vaccination with PPSV23 at Week 8 with 5mL draw for pneumococcal serotype titers as well as a blood draw at Week 16 and Week 24. Immunogenicity will be analyzed by assessing for serotype-specific IgG as well as total IgG binding. Samples will be run at Mayo Rochester, and samples will additionally be shipped to a third party, The Binding Site, for further antipneumococcal binding assays. The samples will be identified to The Binding Site only by their study-specific identification number (i.e. A01, B01 etc). The Binding Site will not receive any patient identifying information.

Resources: *Describe the available resources to conduct the research (personnel, time, facilities, mentor commitment, etc.):*

This study is being conducted by [name], [name], [name], and [name]. [name], PGY4, has 9 months of dedicated research time.

(1a) This is a multisite study involving Mayo Clinic and non Mayo Clinic sites. *When checked, describe in detail the research procedures or activities that will be conducted by Mayo Clinic study staff.*

(1b) Mayo Clinic study staff will be engaged in research activity at a non Mayo Clinic site. *When checked, provide a detailed description of the activity that will be conducted by Mayo Clinic study staff.*

Subject Information

Target accrual is the proposed total number of subjects to be included in this study at Mayo Clinic. A "Subject" may include medical records, images, or specimens generated at Mayo Clinic and/or received from external sources.

Target accrual: 50

Subject population (children, adults, groups): Adults

Inclusion Criteria: Ages 19 to 64 with diagnosis of asthma

Exclusion Criteria: Exclusion criteria include research exemption requested, history of PCV-13 vaccination, age $<$ 19 or $>$ 65, history of cochlear implant, CSF leak, CHF, DM, CKD, HIV, CVID as well as patients

who have received the PPSV23 vaccine in the last 5 years. Women who are pregnant will also be excluded from the study by performing 2 point of care urine pregnancy tests (prior to vaccinations)

Research Activity

Check all that apply and complete the appropriate sections as instructed.

1. **Drug & Device:** Drugs for which an investigational new drug application is not required. Device for which (i) an investigational device exemption application is not required; or the medical device is cleared/approved for marketing and being used in accordance with its cleared/approved labeling. (Specify in the Methods section)
2. **Blood:** Collection of blood samples by finger stick, heel stick, ear stick, or venipuncture.
3. **Biological specimens other than blood:** Prospective collection of human biological specimens by noninvasive means that may include: urine, sweat, saliva, buccal scraping, oral/anal/vaginal swab, sputum, hair and nail clippings, etc.
4. **Tests & Procedures:** Collection of data through noninvasive tests and procedures routinely employed in clinical practice that may include: MRI, surface EEG, echo, ultrasound, moderate exercise, muscular strength & flexibility testing, biometrics, cognition testing, eye exam, etc. (Specify in the Methods section)
5. **Data** (medical record, images, or specimens): Research involving use of existing and/or prospectively collected data.
6. **Digital Record:** Collection of electronic data from voice, video, digital, or image recording. (Specify in the Methods section)
7. **Survey, Interview, Focus Group:** Research on individual or group characteristics or behavior, survey, interview, oral history, focus group, program evaluation, etc. (Specify in the Methods section)

NIH has issued a *Certificate of Confidentiality* (COC). *When checked, provide the institution and investigator named on the COC and explain why one was requested.* _____

Biospecimens – Categories 2 and 3

(2) Collection of blood samples. When multiple groups are involved copy and paste the appropriate section below for example repeat section b when drawing blood from children and adults with cancer.

a. **From healthy, non-pregnant, adult subjects who weigh at least 110 pounds.** For a minimal risk application, the amount of blood drawn from these subjects may not exceed 550ml in an 8 week period and collection may not occur more frequently than 2 times per week.

Volume per blood draw: 15 ml

Frequency of blood draw (e.g. single draw, time(s) per week, per year, etc.) 4 times per year _____

b. **From other adults and children considering age, weight, and health of subject.** For a minimal risk application, the amount of blood drawn from these subjects may not exceed the lesser of 50 ml or 3 ml per kg in an 8 week period, and collection may not occur more frequently than 2 times per week.

Volume per blood draw: 15 ml

Frequency of blood draw (e.g. single draw, time(s) per week, per year, etc.) _____

(3) Prospective collection of biological specimens other than blood: _____

Review of medical records, images, specimens – Category 5

For review of existing data: provide a date range or an end date for when the data was generated. The end date can be the date this application was submitted to the IRB. Example: *01/01/1999 to 12/31/2015* or all records through *mm/dd/yyyy*.

Date Range:

Check all that apply (data includes medical records, images, specimens).

(5a) Only data that exists before the IRB submission date will be collected.

(5b) The study involves data that exist at the time of IRB submission **and** data that will be generated after IRB submission. Include this activity in the Methods section.

Examples

- The study plans to conduct a retrospective chart review and ask subjects to complete a questionnaire.
- The study plans to include subjects previously diagnosed with a specific disease and add newly diagnosed subjects in the future.

(5c) The study will use data that have been collected under another IRB protocol. Include in the Methods section and enter the IRB number from which the research material will be obtained. *When appropriate, note when subjects have provided consent for future use of their data and/or specimens as described in this protocol.*

Enter one IRB number per line, add more lines as needed

Data Specimens Data & Specimens _____

Data Specimens Data & Specimens _____

Data Specimens Data & Specimens _____

(5d) This study will obtain data generated from other sources. Examples may include receiving data from participating sites or an external collaborator, accessing an external database or registry, etc. Explain the source and how the data will be used in the Methods section.

(6) Video audio recording: *Describe the plan to maintain subject privacy and data confidentiality, transcription, store or destroy, etc.*

HIPAA Identifiers and Protected Health Information (PHI)

Protected health information is medical data that can be linked to the subject directly or through a combination of indirect identifiers.

Recording identifiers (including a code) during the conduct of the study allows you to return to the medical record or data source to delete duplicate subjects, check a missing or questionable entry, add new data points, etc. De-identified data is medical information that has been stripped of all HIPAA identifiers so that it cannot be linked back to the subject. De-identified data is **rarely** used in the conduct of a research study involving a chart review.

Review the list of subject identifiers below and, if applicable, check the box next to each HIPAA identifier being recorded at the time of data collection or abstraction. Identifiers apply to any subject enrolled in the study including Mayo Clinic staff, patients and their relatives and household members.

Internal refers to the subject's identifier that will be recorded at Mayo Clinic by the study staff.

External refers to the subject's identifier that will be shared outside of Mayo Clinic.

Check all that apply:	INTERNAL	EXTERNAL
Name	x	
Mayo Clinic medical record or patient registration number, lab accession, specimen or radiologic image number	x	
Subject ID, subject code or any other person-specific unique identifying number, characteristic or code that can link the subject to their medical data	x	x
Dates: All elements of dates [month, day, and year] directly related to an individual, their birth date, date of death, date of diagnosis, etc.	x	
Note: Recording a year only is not a unique identifier.		
Social Security number		
Medical device identifiers and serial numbers		
Biometric identifiers, including finger and voice prints, full face photographic images and any comparable images		
Web Universal Resource Locators (URLs), Internet Protocol (IP) address numbers, email address		
Street address, city, county, precinct, zip code, and their equivalent geocodes		
Phone or fax numbers		
Account, member, certificate or professional license numbers, health beneficiary numbers		
Vehicle identifiers and serial numbers, including license plate numbers		
Check 'None' when none of the identifiers listed above will be recorded, maintained, or shared during the conduct of this study. (exempt category 4)	 None	 None

Data Analysis

Power analyses and study endpoints are not required for minimal risk research, pilot or feasibility studies.

No statistical information. *If checked, please explain:*

Data Analysis:

For each of the 23 serotypes, exact, unconditional, 2-sided 95% confidence intervals (CIs) on the single proportions will be calculated using the F distribution. The 95% CIs for the difference in proportions ([PCV-13+PPSV23] – [PPSV23]) will be computed using the non-inferiority procedure of Chan and Zhang, using the standardized test statistic and $\gamma=0.000001$. Non-inferiority is declared if the lower CI for the difference is >-0.10 . Similar procedures will be used for the evaluation of antibody concentrations after 12 months.

For the secondary endpoints, the pneumococcal IgG serotype antibody concentrations will be logarithmically transformed for analysis. Within each treatment group and for each antibody concentration separately, geometric means of the antibody concentrations will be calculated for each vaccine group. Two (2)-sided 95% CIs will be constructed by back transformation of the CIs for the mean of the logarithmically transformed assay results will be computed using the Student *t* distribution. To assess differences between the 2 vaccine groups, the 95% CIs for geometric mean ratio will be computed using the Student *t* distribution for the mean difference of the measures on the log scale ([PCV-13+PPSV23] – [PPSV23]) Non-inferiority will be declared if the lower limit of the CI for the ratio was greater than 0.5 (2-fold criterion). In addition, the geometric mean fold rises from baseline to 12 month following PPSV23 in each arm, and corresponding 2-sided 95% CIs, will be calculated for each of the serotype-specific pneumococcal IgG responses. For formulation decision analyses, 99.8% CIs will be calculated.

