Immunogenicity of PPSV-23 after PCV-13 Vaccination in Adult Asthmatic Patients

NCT03260790

6/7/2018

IRB Minimal Risk Protocol Template

Note: If this study establishes a human specimen repository (biobank) for research purposes, do not use this template. Use the Mayo Clinic Human Specimen Repository Protocol Template found on the IRB home page under Forms and Procedures at <http://intranet.mayo.edu/charlie/irb/>

First-time Use: Use this template to describe your study for a new IRB submission.

1. Complete the questions that apply to your study.
2. Save an electronic copy of this protocol for future revisions.
3. When completing your IRBe application, you will be asked to upload this document to the protocol section.

Modification: To modify this document after your study has been approved:

1. Open your study in IRBe. Click on the study 'Documents' tab and select the most recent version of the protocol. Save it to your files.
2. Open the saved document and activate "Track Changes".
3. Revise the protocol template to reflect the modification points , save the template to your files
4. Create an IRBe Modification for the study and upload the revised protocol template.

General Study Information

Principal Investigator: [name]

Study Title: **Immunogenicity of PPSV-23 after PCV-13 Vaccination in Adult Asthmatic Patients**

Protocol version number and date: Protocol version number 3. 06/07/2018

Research Question and Aims

Hypothesis:

- 1) Priming with PCV13 will result in increased immunogenicity of PPSV23 in asthmatic subjects
- 2) Priming with PCV13 will result in durable immunogenicity of the PPSV23 in asthmatic subjects

Aims, purpose, or objectives:

Aim 1 will compare the safety and immunogenicity of PPSV23 and PCV13 vaccines in asthmatic subjects. The vaccine response of randomized asthmatic patients to either PPSV 23 alone (Group A) or PCV13 with PPSV23 given 8 weeks later (Group B) will be compared. Immunogenic response will be assessed and compared between groups at 8 and 16 weeks after vaccination.

Aim 2 will compare the changing of immunologic response in the two arms over the subsequent 8 weeks' time frame in both Group A and Group B.

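### If the letter in sample IDs such as A01 and B01 is the randomized group, as the text most naturally reads, the outside assay laboratory can sort its samples by arm

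*Combined protocol and SAP*

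**What the plan says.** Under Study Design and Methods, the Protocol paragraph has patients "randomized into either Group A (standard of care) or Group B (experimental group"). Research Question and Aims gives the regimen behind each letter: "either PPSV 23 alone (Group A) or PCV13 with PPSV23 given 8 weeks later (Group B").

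The same Protocol paragraph has samples run at Mayo Rochester and adds that "samples will additionally be shipped to a third party, The Binding Site, for further antipneumococcal binding assays". On labelling it says: "The samples will be identified to The Binding Site only by their study-specific identification number (i.e. A01, B01 etc"). The one protection stated for the shipped material is that "The Binding Site will not receive any patient identifying information".

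The section on HIPAA identifiers defines the External column as the "identifier that will be shared outside of Mayo Clinic". The row marked in that column is "Subject ID, subject code or any other person-specific unique identifying number, characteristic or code that can link the subject to their medical data".

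The document does not define the letter in the ID. It does not provide for recoding before shipment, or for masking of any laboratory or assessor.

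**The concern.** The two letters shown in the example IDs are the two letters that name the arms, and both appear in the same paragraph. If the prefix is the arm, assay staff see the grouping while they produce results that may be compared between those groups.

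What is at stake is the ordinary protection against assay bias. Staff who can see the grouping may, without intending to, handle, repeat or query samples differently by group. This is a general concern: the document describes no reading rule or discretionary step for these assays through which it would act. A code that hides the patient's identity does nothing to hide the arm.

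**Working it through.** The plan states no figure on this point, so there is none to reproduce. The check is a reading of the text, followed by a count of the samples exposed.

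**What the letter means**

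1. The arms are Group A and Group B (Protocol paragraph).
2. The example IDs are A01 and B01 (same paragraph). Only the letters A and B are shown.
3. Both examples carry the number 01. That fits numbering within group; a single running sequence of subject numbers would not repeat 01.
4. No other meaning is given anywhere. A letter for recruitment source or draw occasion is conceivable and could also repeat 01, but nothing in the text suggests either.
5. Reading the letter as the arm is therefore the most natural interpretation. It remains an inference.

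**What follows if the letter is the arm**

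1. The prefix alone sorts each shipped sample into one of two sets.
2. Knowing which set is experimental also needs the group definitions. The document does not say whether the laboratory has them.
3. The assurance about patient identifying information covers privacy. The entry in the HIPAA table shows that a code leaves the institution, not that the code reveals the arm.

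**Which results are exposed**

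1. The labelling statement covers only samples sent to the outside laboratory. Labels used for the runs at Mayo Rochester are not described, so the point cannot be extended to them.
2. Data Analysis covers proportions ("For each of the 23 serotypes, exact, unconditional, 2-sided 95% confidence intervals (CIs) on the single proportions") and log-transformed serotype-specific IgG concentrations. It names no analysis of the additional binding assays.

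**How many samples**

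Inputs: target accrual 50 (Subject Information); draws at weeks 0, 8, 16 and 24, so 4 per subject (Protocol paragraph). The number of draws shipped per subject is not stated, so it is varied here as an assumption.

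Formula: samples = subjects × draws shipped per subject.

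| Draws shipped per subject (assumed) | Samples at most |
|---|---|
| 1 | 50 × 1 = 50 |
| 2 | 50 × 2 = 100 |
| 3 | 50 × 3 = 150 |
| 4 | 50 × 4 = 200 |

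If all four are shipped, 50 are week-0 pre-vaccination samples and 50 × 3 = 150 come after the first vaccination. These are upper limits, since they assume full accrual and no missed draws. They count exposed samples and do not measure bias.

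**The case against.** The case for leaving this out is reasonable.

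- **The premise is inferred.** Nowhere is the letter said to be the arm. This stands, and it is why the point is conditional.
- **Separating is not decoding.** Expectation-driven bias also needs to know which letter is experimental, and the laboratory may not have been told. This also stands, although the ability to group samples is already a loss of masking and the key is printed in the protocol.
- **No planned analysis is shown to be affected.** The outside assays are additional, and Data Analysis does not mention them. This stands as to the non-inferiority comparisons. It does not make the outside results irrelevant: the Protocol paragraph lists both serotype-specific IgG and total IgG binding as immunogenicity measures, and does not say which laboratory produces which.
- **No blinding was promised.** Correct, so nothing is contradicted. But Group B has a second vaccination at week 8 and no placebo is described for Group A, so masking of patients or clinic staff is not part of the design. Masking the assay is an easy safeguard that remains available.
- **Relabelling has its own risk.** If IDs have already been issued, the items to relabel are samples and not only subject codes, and a transcription error could mix them up. That is fair and belongs in the cost.
- **The HIPAA table is flattened in the available text.** The column of a single mark is read from its order. The point does not depend on that table.

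These objections limit the point to a minor one. They do not remove it, because following the stated labelling would most naturally let the laboratory sort samples by arm.

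**Conclusion.** The concern holds as a conditional, minor weakness of design. If the letter is the randomized group, the outside laboratory can separate by arm every sample it receives, and nothing in the plan prevents this. The size of any bias cannot be estimated from the documents, and no effect on the planned non-inferiority comparisons is shown.

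The conclusion rests on one inference, that the prefix denotes the group. Confidence is medium for that reason. The point earns its place because the remedy is cheap.

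**What to change.** Ship samples under arm-neutral codes. Either assign sequential subject numbers, for example 001 to 050, before randomization, or apply separate codes before shipment. Keep the code-to-arm list from assay staff, and state both steps in the Methods. If the letter does not denote the group, one sentence saying what it does denote is enough.

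The cost is a small labelling and key-keeping task for at most 50 subject codes. If IDs have already been issued, up to 200 sample labels would need recoding with a checked transcription step to guard against mix-ups; whether they have been issued is not stated. No extra draws, tests or storage are needed, and the HIPAA entry for an externally shared subject code can stay as it is.

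### The lead analysis compares an undefined per-serotype proportion and leaves the log-concentration comparison secondary; a baseline-adjusted geometric mean ratio should lead, with a rule that can show an increase

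*Combined protocol and SAP*

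**What the plan says.** The Protocol paragraph of Study Design and Methods gives the outcome: "Immunogenicity will be analyzed by assessing for serotype-specific IgG as well as total IgG binding". Serotype titres are drawn at week 0 as a pre-vaccination measure, and again at weeks 8, 16 and 24.

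The Data Analysis section starts with proportions: "For each of the 23 serotypes, exact, unconditional, 2-sided 95% confidence intervals (CIs) on the single proportions will be calculated using the F distribution". It then compares the arms: "The 95% CIs for the difference in proportions ([PCV-13+PPSV23] – [PPSV23]) will be computed using the non-inferiority procedure of Chan and Zhang". The decision rule is "Non-inferiority is declared if the lower CI for the difference is >-0.10". The event that the proportion counts is not defined, and no threshold or fold-rise rule is given.

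The log-scale analysis follows under a different label: "For the secondary endpoints, the pneumococcal IgG serotype antibody concentrations will be logarithmically transformed for analysis". It gives a between-arm GMR with a Student t interval and declares non-inferiority if the lower limit exceeds 0.5. Fold rises from baseline are planned within each arm only. Baseline adjustment of the between-arm GMR is not mentioned.

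Hypothesis 1, under Research Question and Aims, is directional: "Priming with PCV13 will result in increased immunogenicity of PPSV23 in asthmatic subjects". Subject Information gives the size: "Target accrual: 50".

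**The concern.** The word primary does not appear, but only the log-concentration analysis is called secondary, so the proportions are the leading analysis by the plan's own ordering. If the proportion is a responder cut of IgG, it discards how far each titre lies above or below the cut. If most of Group A already responds, a ceiling also leaves little room for an increase to show.

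Hypothesis 1 asks whether the response is larger. With 50 subjects, the leading comparison could miss an increase that the same samples would show on the log scale. Promoting the GMR after the results are known would be open to criticism, so the order needs to be settled beforehand.

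**Working it through.** The plan states no power and no derivation of its sample size, so there is no figure to reproduce. The check compares the two scales on the same question: is Group B higher than Group A?

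**Inputs from the documents.** Total 50; two-sided 95% intervals, so 2.5% at the lower limit; Student t on the log scale; exact unconditional comparison of proportions.

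**Assumptions not in the documents.** 1:1 allocation (25 per arm), no dropout, log-normal titres with equal SD, SD 0.5 log10 (range 0.4 to 0.6), true GMR 2 (range 1.5 to 3), Group A response 30% to 90%, and a responder defined by an absolute cut on the same post-vaccination titre that the GMR uses.

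**Log scale.** The noncentrality is log10(2) / (0.5 × √(2/25)) = 0.301 / 0.1414 = 2.13. With 48 degrees of freedom the critical value is 2.01, and the noncentral t distribution gives power 55.0%.

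**Proportions.** The Group B rate is Φ(Φ⁻¹(pA) + log10(GMR)/SD), a shift of 0.301/0.5 = 0.602. All 26 × 26 outcomes were enumerated with the score statistic at zero difference. The rejection region was set so that the maximum size over the nuisance rate stays at or below 0.025 (achieved 0.023).

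| Group A rate | Group B rate | Power, proportions | Power, log scale | Loss (points) |
|---|---|---|---|---|
| 30% | 53.1% | 35.4% | 55.0% | 19.6 |
| 50% | 72.6% | 35.9% | 55.0% | 19.1 |
| 70% | 87.0% | 27.6% | 55.0% | 27.4 |
| 80% | 92.6% | 20.9% | 55.0% | 34.1 |
| 90% | 97.0% | 11.5% | 55.0% | 43.5 |

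**Range.** Over SD 0.4 to 0.6, GMR 1.5 to 3 and Group A rates 30% to 90%, the log scale was better in every case under the absolute cut. The smallest gap was 17.3% − 11.6% = 5.7 points (SD 0.6, GMR 1.5, rate 30%). The largest was 98.5% − 20.1% = 78.4 points (SD 0.4, GMR 3, rate 90%).

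**Fold-rise responder.** If response means a rise from week 0, the relevant SD is that of the change, 0.5 × √(2(1 − r)), where r is the baseline to post-vaccination correlation (assumed; the documents give none).

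- At r = 0.5 this SD is again 0.5, so the proportion powers equal those in the table.
- At r = 0.7 it is 0.387, and proportion power is 53%, 54%, 41%, 31% and 15% at Group A rates of 30%, 50%, 70%, 80% and 90%.
- At r = 0.8 it is 0.316, and proportion power is 71%, 71%, 53%, 40% and 17%.

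The unadjusted GMR stays at 55%, so at r = 0.8 it is beaten at rates of 30% and 50%. On the log scale at r = 0.8, a comparison of changes has 91% power. Analysis of covariance on the week 0 titre, with residual SD 0.5 × √(1 − 0.8²) = 0.30, has about 93%. Both exceed the 71%.

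**The case against.** The strongest objection is that the cut of IgG is inferred. The plan speaks of proportions without saying what they count, and undefined response is arguably the more basic defect. That stands, and the point is worded accordingly. The inference is still reasonable: IgG is the measured outcome, and the same paragraph applies similar procedures to antibody concentrations at a later time.

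A reader might infer that the loss is 19 to 44 points whichever responder definition is used. The documents do not support that. The figure belongs to one assumed SD, effect and allocation with an absolute cut, and a fold-rise definition with high baseline correlation can reverse it against the unadjusted GMR. What survives is narrower: on the same variable, the log scale did better than its own cut in every case tried.

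A reader might also infer that exchanging the order of the two analyses is enough. It is not. The only rule attached to the GMR is a lower limit above 0.5. An interval from 0.6 to 1.5 would meet it without showing any increase.

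The power figures are for a superiority criterion, whereas both planned rules are non-inferiority. That is fair, but superiority is what Hypothesis 1 needs. Under the planned rules with no true difference, approximate power is 10% to 22% for proportions and 57% to 76% for the GMR at SD 0.4 to 0.5 log10 (55% to 74% by exact t). The two margins are not equivalent, so this is only supporting evidence.

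Finally, both analyses are prespecified and the form says that power analyses and endpoints are not required for minimal risk research. It would be wrong to say that the log-scale information is lost. The issue is which analysis answers Hypothesis 1, and settling that needs no power calculation.

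**Conclusion.** The concern holds in qualified form. The leading analysis is a per-serotype proportion, undefined and most naturally a responder cut of IgG, while the full-scale comparison is secondary. For the same variable, dichotomising costs power for Hypothesis 1: 55% against 12% to 36% per serotype in the illustrative case, and about 6 to 78 points over the wider range. These sizes rest on assumed SD, effect, response rates, 1:1 allocation and an absolute cut, none of which the documents give. They are per serotype and are not the power of an overall conclusion across 23 serotypes, for which the plan gives no combining rule. The unadjusted GMR is not superior to every possible responder definition. In the fold-rise case where it fell behind, the baseline-adjusted log-scale comparison kept the advantage.

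**What to change.** In Data Analysis:

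- Make the between-arm GMR of log-transformed serotype-specific IgG, adjusted for the week 0 log titre by analysis of covariance, the lead analysis.
- Conclude increased immunogenicity (Hypothesis 1) for a serotype only if the lower 95% limit of the GMR is above 1. Keep the 0.5 limit for non-inferiority only.
- State what the responder proportion counts, and report the proportions and their difference as supportive estimates with confidence intervals.

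The change is to the analysis text: a reordering, one covariate and one decision rule. The week 0 titre is already drawn, so no samples, assays or subjects are added. The downside is small. The responder rate, which is easier to read clinically, becomes supportive, and the log scale relies on approximate normality and on a stated handling of values at the assay limits.
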